3.1.4 Post-Treatment Follow-Up: Safety and Long-term

A safety follow-up visit will be scheduled within 28 days (+/- 7 days) following last treatment (See [Study Calendar](#) for further details and assessments).

Subsequent post-treatment follow-up will occur every 3 months (+/- 2 weeks) starting after the safety visit, for the first year, then every 6 months (+/- 4 weeks) for years 2 – 5, and then annually (+/- 6 weeks) thereafter, at the discretion of the investigator (See [Study Calendar](#) for further details and assessments).

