3. Every odd numbered week for up to 51 weeks. Allowance for scheduling changes: Brief changes (up to 1 days earlier or up to 3 days later) in bintrafusp alfa administration and indicated evaluations may occasionally be required due to travel delays or restrictions, airport closure, inclement weather, family responsibilities, security alerts, government holidays, complications of disease not attributable to disease progression or protocol therapy, etc. These delays will not be considered protocol deviation. The timing of subsequent bintrafusp alfa administrations will be adjusted to maintain a minimum interval of 11 days between bintrafusp alfa administrations. Any dose that cannot be accommodated within this window will be skipped and the dose not made up. In the event of a durable PR or CR after one year on trial, further treatment may be held (even if a total of 26 doses has not been given) and scheduled assessments may be performed at 3-month (+/- 2 weeks) intervals at the discretion of the investigator.
4. End of Treatment visit (EOT): within 14 days of the decision to discontinue treatment prematurely before completion of 26 doses. Clinical Center clinic visit preferred; if the participant cannot return to the Clinical Center for this visit, a request will be made to collect required clinical labs (specify as needed) from a local physician or laboratory. If this is not possible, participants may be assessed by telephone/email for symptoms. Does not need to be completed if drug is withheld after 26 doses.
5. 28 days (+/- 7 days) following last treatment. Clinical Center clinic visit preferred; if the participant cannot return to the Clinical Center for this visit, they may be assessed by telephone/email for adverse events.

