6. Subsequent Post-treatment follow-up: Every 3 months (+/- 2 weeks), starting after the safety visit for the first year, followed by every 6 months (+/- 4 weeks) for years 2-5, and then annually (+/- 6 weeks) thereafter at the discretion of the investigator. Follow-ups may be done by phone/email or by clinic visit at the discretion of the investigator. Follow-up via telephone/email will include survival, adverse events, and assessment of further tumor therapy; furthermore, routine outside blood, urine, and imaging results may be collected and used for analysis at the discretion of the investigator. Any other evaluations and tests should be performed as clinically indicated. Participants who have not progressed on treatment will be scanned until progression. Those that completed the previous 26-doses course and have progression will be invited for an additional course (26 doses) at the time of progression.
7. Bintrafusp alfa administered IV at flat dose of 1,200 mg.
8. As indicated in Section **12.3**, all subjects will be offered the opportunity to complete an NIH advance directive form. This should be done preferably at baseline but can be done at any time during the study as long as the capacity to do so is retained. The completion of the form is strongly recommended but is not required.
9. Every 6 weeks.
10. Imaging (Section **6.3**) will be performed every 8 weeks (+/- 1 week). In the event of a PR or CR, tumor imaging assessments may be performed every 3 months (+/- 2 weeks) at the discretion of the investigator. Tumor assessment should be continued beyond end of treatment in participants who have not experienced PD until they experience PD in order to assess PFS. Additional imaging to be performed at the investigator's discretion. Imaging performed in outside facilities maybe utilized in the case of travel restrictions or delays, airport closures, inclement weather, family responsibilities, security alerts and government holidays, etc. Nuclear bone scan or imaging may be done for individuals with known/suspected bone lesions at screening; in these cases bone scans should be done in follow-up for response assessments.
11. Optional biopsies: at baseline (within 2 weeks prior to first treatment) and within 2 weeks of first imaging restaging; optional biopsy at/near progression, where clinically feasible.

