6 DATA COLLECTION AND EVALUATION

6.1 DATA COLLECTION

The PI will be responsible for overseeing entry of data into a 21 CFR Part 11-compliant data capture system provided by the NCI CCR and ensuring data accuracy, consistency and timeliness. The principal investigator, associate investigators/research nurses and/or a contracted data manager will assist with the data management efforts. Primary and final analyzed data will have identifiers so that research data can be attributed to an individual human subject participant.

All adverse events, including clinically significant abnormal findings on laboratory evaluations, regardless of severity, will be followed until return to baseline or stabilization of event.

Document AEs from the first study intervention, study day 1, through 28 days after the subject received the last product administration. After 28 days, only adverse events which are serious and related to the study investigational agent need to be recorded.

An abnormal laboratory value will be recorded in the database as an AE **only** if the laboratory abnormality is characterized by any of the following:

- Results in discontinuation from the study
- Is associated with clinical signs or symptoms
- Requires treatment or any other therapeutic intervention
- Is associated with death or another serious adverse event, including hospitalization.
- Is judged by the Investigator to be of significant clinical impact
- If any abnormal laboratory result is considered clinically significant, the investigator will provide details about the action taken with respect to the test drug and about the participant's outcome.

End of study procedures: Data will be stored according to HHS, FDA regulations, and NIH Intramural Records Retention Schedule as applicable.

Loss or destruction of data: Should we become aware that a major breach in our plan to protect subject confidentiality and trial data has occurred, this will be reported expeditiously per requirements in Section [7.2.1](#).

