8.1.6 Adverse Events of Special Interest (AESI)

An adverse event of special interest (AESI) is one of scientific and medical interest specific to understanding of the Investigational Product(s) and may require close monitoring and rapid communication by the investigator to the sponsor. An AESI may be serious or non-serious. The rapid reporting of AESIs allows ongoing surveillance of these events to characterize and understand them in association with the use of these investigational products.

Only AESIs that match the definition of SAE will be reported as other SAEs within 7 days from the knowledge of event. Other non-SAE AESIs should not be reported to OSRO but only collected in the clinical database.

The adverse events related to following, regardless of site, will be collected as an AESI to enable evaluation of potential risk factors, such as site/past radiation/associated infection at site/recent instrumentation and other variables such as time to onset, exposure history, grade of bleeding, anatomical sites, etc. can be collected.

- Mucosal bleeding
- Cutaneous lesions possibly due to TGF-beta

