12.2 PARTICIPATION OF CHILDREN

Individuals under the age of 18 will not be eligible to participate in this study because of unknown toxicities in pediatric participants.

The effects of bintrafusp alfa on the developing human fetus are unknown. For this reason and because immunotherapeutic agents as well as other therapeutic agents used in this trial may be teratogenic, women of child-bearing potential and men must agree to use highly effective contraception (hormonal or barrier method of birth control; abstinence) prior to study entry and up to 65 days for women and 125 days for men following the last dose of any study treatment. Should a woman become pregnant or suspect she is pregnant while she or her partner is participating in this study, she should inform her treating physician immediately.

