- Anemia (29%)
- Decreased appetite (25%)

- Fatigue (tiredness) (22%)
- Pruritus (itching) (21%)
- Dyspnea (shortness of breath) (21%)
- Constipation (19%)
- Nausea (19%)
- Pyrexia (fever) (19%)
- Asthenia (weakness, fatigue) (17%)
- Diarrhea (16%)
- Abdominal pain (15%)
- Vomiting (14%)
- Cough (13%)
- Headache (12%)
- Epistaxis (12%)
- Rash (11%)
- Elevation of aspartate aminotransferase (AST, liver enzyme) (11%)
- Leg or arm swelling (10%)

Skin-related adverse events which were possibly due to TGF- β inhibition, occurred in 11% of participants and included keratoacanthomas (7%), squamous cell carcinoma of the skin (3%), and hyperkeratosis (1%) and are important identified risks with bintrafusp alfa.

Anemia, alterations in wound healing or repair of tissue damage, and embryofetal toxicity remain important potential risks.

At least 2 instances of nodular regenerative hyperplasia have been observed with the use of this agent.

In addition, mucosal bleeding events (e.g. gum bleeding, nose bleeds, coughing up blood, blood in urine or stool) are a potential risk for bintrafusp alfa, included in the informed consent document.

Infusion-related Reactions (including reactions, signs and symptoms) occurred in 38 (6%) participants in the pooled safety analysis, and all IRRs were of Grade 1 or 2 intensity; most of the IRRs had an onset after the first or second infusion; those with onset after the third infusion (or later) were less frequent. Consequently, the administration of premedication is not required. As per Section 3.2.3, if an Investigator deems necessary to administer a premedication to a particular participant, an antihistamine (e.g. 25 to 50 mg diphenhydramine) and paracetamol (acetaminophen, 500 to 650 mg intravenously or equivalent oral dose) 30 to 60 minutes prior to bintrafusp alfa infusion is recommended. Premedication should be administered for subsequent bintrafusp alfa doses based upon clinical judgment and presence/severity of prior infusion reactions. This regimen may be modified based on local treatment standards and guidelines as appropriate provided it does not include systemic corticosteroids.

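### After day 28 only serious and related adverse events must be recorded, so late non-serious skin, bleeding and immune-related events are asked about at follow-up but can be missing from the safety tables

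*Combined protocol and SAP*

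**What the plan says.** - **Recording window.** Section 6.1 of the combined protocol and SAP sets the full window: "Document AEs from the first study intervention, study day 1, through 28 days after the subject received the last product administration". Beyond that: "After 28 days, only adverse events which are serious and related to the study investigational agent need to be recorded". An event must meet both conditions before recording is required.
- **AESIs.** Section 8.1.6 names two: mucosal bleeding, and skin lesions possibly caused by TGF-beta inhibition. It says they may be non-serious, and it wants them collected so that risk factors and variables such as time to onset and exposure history can be evaluated. On handling: "Other non-SAE AESIs should not be reported to OSRO but only collected in the clinical database". Immune-related events are not on this list.
- **Link between the two.** Section 8.2 sends the reader to 6.1 for the recording timeframe.
- **Long-term follow-up.** Footnote 6 of the study calendar: "Follow-up via telephone/email will include survival, adverse events, and assessment of further tumor therapy". The Adverse Events row has four marks, which fit Week 1, later weeks, end of treatment and the safety visit. None falls under Long Term.
- **Analysis.** Section 10.4.3 tabulates treatment-emergent events and serious events by grade. It does not define treatment-emergent or give it a time limit.

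**The concern.** Safety and tolerability is a stated secondary objective (1.1.2). Because 10.4.3 does not define treatment-emergent, the recording rule in 6.1 in practice decides what is counted. The calendar footnote tells staff to ask about adverse events at long-term contacts, while 6.1 does not oblige them to keep a non-serious answer. The events most exposed to this are the two AESIs and immune-related events, which Section 14.1.2 presents as characteristic of this drug and its class. Many of them would be managed without admission.

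With at most 32 participants, each of these categories is expected to hold only a few cases, so one omission changes a reported rate visibly. The stated purpose of collecting AESIs, including time to onset, is also weakened if recording of non-serious late onsets depends on the habits of whoever makes the call.

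**Working it through.** The plan states no figure on this point, so there is nothing to reproduce. The check has two parts.

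**1. The rules side by side**

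| Onset after last dose | Serious and related | Any other event |
|---|---|---|
| Day 0 to 28 | Must be recorded (6.1) | Must be recorded (6.1) |
| After day 28 | Must be recorded (6.1) | Need not be recorded (6.1; AESIs too, through 8.2) |

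The lower right cell is the gap. Footnote 6 covers the same period and brings adverse events into the contact. The calendar row does not mark it. The marks are read from a table that lost some of its layout, but their number and position fit no Long Term entry.

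**2. When the contacts fall**

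The safety visit is "28 days (+/- 7 days) following last treatment": 28 - 7 = day 21 to 28 + 7 = day 35. The first long-term contact is 3 months (about 91 days) +/- 14 days after that visit:

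- safety visit on day 21: 21 + 91 +/- 14 = day 98 to 126
- safety visit on day 28: day 105 to 133
- safety visit on day 35: day 112 to 140

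**3. Illustration of size**

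Inputs: N = 32, the accrual ceiling (10.2). Rates from 14.1.2: TGF-beta skin events 11%, epistaxis 12% (a rough stand-in for mucosal bleeding), immune-related events 21.7%. Late and non-serious share s = 5% to 30%. This share is an assumption; the documents give none.

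Expected participants = N x rate. Unrecorded = N x rate x s. Chance of at least one = 1 - (1 - rate x s)^N.

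| Event | N x rate | Unrecorded, s = 5% to 30% | Chance of at least one |
|---|---|---|---|
| Skin | 32 x 0.11 = 3.5 | 0.2 to 1.1 | 16% to 66% |
| Epistaxis | 32 x 0.12 = 3.8 | 0.2 to 1.2 | 18% to 69% |
| Immune-related | 32 x 0.217 = 6.9 | 0.3 to 2.1 | 30% to 88% |

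If both cohorts stop after stage 1, N = 12 + 5 = 17 and the unrecorded numbers fall to 0.09-0.56, 0.10-0.61 and 0.18-1.11.

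One input is itself inconsistent. Section 14.1.2 attaches 21.7% to 137 of 630 participants in one place and to 123 of 630 in another. 137/630 is 21.7%, but 123/630 is 19.5%. With 19.5% the expected number is 32 x 0.195 = 6.2, and the unrecorded number is 0.3 to 1.9.

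**The case against.** The strongest reply is that the plan sets one window, states it openly and applies it to all events, and that the safety analysis is secondary and descriptive. Much of this stands:

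- The wording of 6.1 is a minimum. Later non-serious events may be recorded; they are just not required.
- Events that start by day 28 remain recordable and are followed to baseline or stabilization. Only new late onsets are affected.
- Participants who have not progressed continue tumor assessment (calendar footnotes 6 and 10), so they are not out of contact between the safety visit and month 3. Those assessments are not marked as adverse event assessments.

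A reader might also infer stronger points that the documents do not support:

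- **That a safety visit on day 21 closes the window early.** Section 3.1.4 allows it: "A safety follow-up visit will be scheduled within 28 days (+/- 7 days) following last treatment". But 6.1 counts days since the last dose, not visits. An event on days 22 to 28 must still be recorded and can be captured at a later contact. This is a visit gap, not a recording cut-off.
- **That the contraception periods show the drug can cause these events for months.** Section 12.2 requires contraception "prior to study entry and up to 65 days for women and 125 days for men following the last dose of any study treatment", but ties it to fetal effects and possible teratogenicity. It says nothing about late skin, bleeding or immune-related onset.
- **That 8.1.6 contradicts 6.1 by setting no time limit.** Section 8.2 supplies the limit.
- **That a late skin cancer would go unrecorded.** Under 8.1.2, an important medical event that may need medical or surgical intervention can be serious, so a related skin cancer may qualify.
- **That the skin rate would be understated by a quarter to a third.** That figure holds only if exactly one of three or four cases is missed, and nothing in the documents shows that one would be. Appendix B says keratoacanthomas may resolve within weeks of stopping the drug, which concerns resolution and not onset.

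**Conclusion.** The core point holds. New non-serious mucosal bleeding, TGF-beta skin lesions and immune-related events after day 28 fall within what long-term contacts ask about, need not be recorded, and can be left out of the 10.4.3 tables. This sits poorly with the purpose that 8.1.6 gives for collecting non-serious AESIs.

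The size is unknown. The ranges above, from about 0.2 up to 2.1 participants per event type at N = 32, rest on an assumed late and non-serious share of 5% to 30%. They also rest on pooled rates from other cohorts, whose post-dose collection window the documents do not give, and on full accrual. The primary analysis of response rate, the sample size and the error rates are not affected. This is a low-cost improvement to a secondary endpoint and not a fault that undermines the trial.

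**What to change.** 1. In 6.1, add that AESIs (8.1.6) and immune-related adverse events are recorded regardless of seriousness through the first long-term contact already planned (3 months +/- 2 weeks after the safety visit), or until new systemic anticancer therapy starts, whichever is earlier.
2. Mark that contact in the Adverse Events row of the study calendar, so that the row, footnote 6 and 6.1 agree.
3. In 10.4.3, tabulate these events on a separate post-28-day line. The 28-day tables then stay as they are.

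**Cost:** protocol wording and a few more database entries from contacts that already take place, with no added visit. Attribution is harder so long after the last dose, which the new-therapy cut-off limits but does not remove. Reported rates may look slightly less favourable. Participants who start other treatment soon after stopping will contribute little, so the gain may be smaller than the illustration suggests.

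Separately, ask the sponsor to reconcile three windows: the safety visit at 28 +/- 7 days (3.1.4 and calendar footnote 5), the post-treatment skin assessment at 28 +/- 5 days (Appendix B, Table C) and the 28-day adverse event window (6.1). Which visit schedule to adopt is for the sponsor to decide.

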6.2 DATA SHARING PLANS

6.2.1 Human Data Sharing Plan

What data will be shared?

I will share human data generated in this research for future research as follows

- Coded, linked data in an NIH-funded or approved public repository.
- Coded, linked data in BTRIS (automatic for activities in the Clinical Center)
- Identified or coded, linked data with approved outside collaborators under appropriate agreements.

How and where will the data be shared?

Data will be shared through:

- An NIH-funded or approved public repository: clinicaltrials.gov, dbGaP
- BTRIS (automatic for activities in the Clinical Center)
- Approved outside collaborators under appropriate individual agreements.
- Publication and/or public presentations.

When will the data be shared?

- Before publication.
- At the time of publication or shortly thereafter.

6.2.2 Genomic Data Sharing Plan

Unlinked genomic data will be deposited in public genomic databases such as dbGaP in compliance with the NIH Genomic Data Sharing Policy.

6.3 RESPONSE ASSESSMENT

For the purposes of this study, during the study participants should be re-evaluated for response every 8 weeks (+/- 1 week), according to the [Study Calendar](#).

The Investigator may perform scans in addition to a scheduled trial scan for medical reasons or if the Investigator suspects PD.

Tumor assessments may include the following evaluations: physical examination (with photograph and measurement of skin lesions, as applicable); cross-sectional imaging using computed tomography (CT) or magnetic resonance imaging (MRI) scan of the skull base, neck, chest, abdomen, and pelvis; nuclear bone scan for subjects with known/suspected bone lesions; and CT of the skull base and MRI of brain (at baseline and follow ups as clinically warranted based on symptoms/findings per investigator discretion). The preferred method of disease assessment is CT with contrast. If CT with contrast is contraindicated, CT of the chest without contrast and MRI scan of the skull base, neck, abdomen/pelvis is preferred.

Radiologic imaging: Brain MRI/CT at the baseline and if needed at follow ups. CT scan of skull base, neck, chest, abdomen, and pelvis. or MRI.

In addition, PET (FDG or Dotatate) scan will be acquired at the time of first treatment response evaluation, and at/near radiographic progression, where clinically feasible. PET scan may also be acquired per investigator discretion to characterize metabolic activity of lesions (target/non-target/new) beyond cross-sectional measurement-based response categories, such as in cases of, discordant response among lesions, durable partial response, or other indeterminate radiological changes.

For each participant, the Investigator will designate 1 or more of the following measures of tumor status to follow for determining response: CT or MRI images of primary and / or metastatic tumor masses, physical examination findings, and the results of other assessments.

The measure(s) to be chosen for sequential evaluation during the trial have to correspond to the measures used to document the progressive tumor status that qualifies the subject for enrollment.

Post-baseline response assessments should follow the lesions identified at baseline. The same modality of assessment (e.g., CT) used to identify/evaluate lesions at baseline should be used throughout the course of the study unless subject safety necessitates a change (e.g., allergic reaction to contrast media).

To assess the primary endpoint of objective response, tumor lesions will be categorized at baseline to target and non-target lesions and used for comparison with subsequent measurements according to the international criteria proposed by the revised Response Evaluation Criteria in Solid Tumors (RECIST) guideline (version 1.1).[\(1\)](#)

All available images collected during the trial period will be considered. Results for the evaluations will be recorded with as much specificity as possible so that pre- and post-treatment results will provide the best opportunity for evaluating tumor response.

Per RECIST 1.1 initial disease progression should be confirmed by imaging after 4 to 6 weeks (preferably 6 weeks, but not later than 8 weeks).

Per RECIST 1.1 any CR or PR should be confirmed by a repeat imaging assessment no sooner than 4 weeks (preferably at the scheduled 6-week interval). Participants who obtain a confirmation scan do not need to undergo the next scheduled imaging assessment if it is due <4 weeks later; imaging may resume at the subsequent scheduled timepoint.

If progression is based on the occurrence of a new lesion in an area not scanned at Baseline, a further on-study scan 6 weeks later should be considered before performing the 28-Day Safety Follow-up visit.

